8.4.5 Pregnancy

A subject's participation is to be terminated immediately if a pregnancy is supposed (i.e. in case her pregnancy test becomes positive). The investigator must report to the sponsor any pregnancy occurring in a female subject during her participation in this study. The outcome of the pregnancy should be followed up carefully, and any outcome of the mother and the child at delivery should be reported.

If a pregnancy is reported, the investigator will record pregnancy information on the appropriate form and submit it to the sponsor within 24 hours of learning of the female participant pregnancy.

While pregnancy itself is not considered to be an AE or SAE, any pregnancy complication or elective termination of a pregnancy for medical reasons will be reported as an AE or SAE.

Abnormal pregnancy outcomes (e.g., spontaneous abortion, fetal death, stillbirth, congenital anomalies, ectopic pregnancy) are considered SAEs, and will be reported as such.

Any post-study pregnancy-related SAE considered reasonably related to the study intervention by the investigator will be reported to the sponsor as described in Section 8.4.4. While the investigator is not obligated to actively seek this information in former study participants, he or she may learn of an SAE through spontaneous reporting.

For all reports, the forms provided are to be used. The investigator should submit them within the same timelines as an SAE (see Section 10.3.4.). Send the completed pregnancy forms to:

[contact] or [contact] (Germany)

8.5 Pharmacokinetics

PK and pharmacodynamic parameters are not evaluated in this study.

8.6 Genetics or Pharmacogenomics

Genetics are not evaluated in this study.

8.7 Biomarkers

Biomarkers are not evaluated in this study.

8.8 Immunogenicity Assessments

Not Applicable

8.9 Health Economics

Health Economics parameters are not evaluated in this study.

9. Statistical Considerations

9.1 Statistical Hypotheses - Amended

For the comparison of the test gel vs. placebo, the primary efficacy hypothesis to be tested is the equality of Algometry AUC 0-72; the second is the POM VAS AUC 0-72.

9.2 Sample Size Determination - Amended

This is a proof of concept study and therefore a specific statistical power calculation cannot be applied, however, assuming a comparable effect of the test gel vs. diclofenac – as suggested by pharmacological studies-, reference is made to similar studies (Predel, Br J Sports Med 2004;38:318–323), in which the standardized effect sizes of Algometry AUC 0-72 and POM VAS AUC 0-72 were over 1; with 30:15 patients, a drop-out rate of 10%, and a two-sided significance level $\alpha = 5\%$, a power $1 - \beta$ of about 80% is reached.

9.3 Analysis Set - Amended

For the purposes of analysis, the following analysis sets are defined:

| Participant Analysis Set | Description |
|--------------------------|---|
| Intent To Treat (ITT) | All subjects who are randomized and provide at least one measure of primary efficacy parameters after the first application of IMP. |
| Per Protocol (PP) | The Per Protocol population will include all subjects in ITT who complete the study and do not have any major protocol violations. Any exclusion from PP Population will be determined and documented prior to the database lock. The primary efficacy analysis population will be PP population and ITT Population will be secondary. The same analysis on ITT Population will be repeated for the primary and secondary and other efficacy endpoints to assess the robustness of the results based on PP Population. |
| Safety | All randomized subjects who take at least one application of IMP. Safety analyses will be conducted on the safety population. |

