4.4 End of Study Definition

The end of the study is defined as the date of the last visit of the last participant in the study.

A participant is considered to have completed the study if he/she has completed all phases of the study up to Visit 6 as shown in the Schedule of Activities.

5. Study Population

Prospective approval of protocol deviations to recruitment and enrollment criteria, also known as protocol waivers or exemptions are not permitted.

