6.8 Continued Access to Study Intervention after the End of the Study

No study intervention will be available after Visit 6 (Day 11).

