2 DESIGN OF THE CLINICAL TRIAL

The study is a Phase II (proof-of-concept), randomized (2:2:1), double-blind, multi-center, active- and placebo-controlled, parallel group clinical trial to compare the efficacy and safety of 10 % Naproxen Gel versus a 2.32 % diclofenac diethylamine gel and placebo in the treatment of acute soft tissue injuries of the lower extremities, conducted in Germany.

Approximately 100 participants will be screened to achieve 75 randomized to study intervention for an estimated total of 30 evaluable participants per each active cohort and 15 participants in the placebo cohort.

The duration of each patient's participation in the study will be 6 consecutive days (from randomization (V1) to Final Visit (V11)).

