3 TIME SCHEDULE

The study consists of 11 visits: randomization visit (Visit 1, 0 h, Day 1), and post-baseline visits Visit 2 (12 h after first treatment, Day 2), Visit 3 (24 h after first treatment, Day 2), Visit 4 (36 h after first treatment, Day 3), Visit 5 (48 h after first treatment, Day 3), Visit 6 (60 h after first treatment, Day 4) and Visit 7 (72 h after first treatment, Day 4), Visit 8 (84 h after first treatment, Day 5), Visit 9 (96 h after first treatment, Day 5) Visit 10 (108 h after first treatment, Day 6), and final Visit 11 (120 h after first treatment, Day 6). A detailed schedule of Assessments is presented in the CSP, Final Amended Version 4.0 approved 09 November 2021, Chapter 1.3, p. 13.

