14.2 Analysis populations

The following analysis populations will be used for analysis of study data:

Safety population: The safety population will include all randomized patients who received at least one dose of the IMP. Safety (e.g., AEs) will be analyzed in this population.

Intent to treat (ITT)/ Full Analysis Set (FAS): All subjects who are randomized and provide at least one measure of primary efficacy parameters after the first application of IMP.

Per protocol (PP) population: The Per Protocol population will include all subjects in ITT who complete the study and do not have any major protocol violations. Any exclusion from PP Population will be determined and documented prior to the database lock. The primary efficacy analysis population will be PP population and ITT/FAS Population will be secondary. The same analysis on ITT/FAS Population will be repeated for the primary and secondary and other efficacy endpoints to assess the robustness of the results based on PP Population.

Before the study is unblinded, each actual post-baseline visit will be mapped to the target visit time to which it is chronologically closest. The numbering of the actual visits (from Visit 1 to Visit 11) will then be changed as needed to improve the correspondence of the actual visit times to the protocol-specified schedule. Final determinations will also be made and documented before the study is unblinded to address visits that are equidistant to two nominal visit times or any other irregularities.

Before the study is unblinded, the timing of the diary assessments will be reviewed, and assessments will be reclassified into time slots as appropriate to ensure that all assessments in a given comparison were made a comparable amount of time after start of treatment.

	Trial Substance:	BAY H6689	Study No.:	21559
	Short Title:	Acute Soft Tissue of the Lower Extremities	Sponsor:	BAYER HEALTHCARE LLC.

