14.4 Efficacy

14.4.1 Primary efficacy variable

The primary efficacy variable is:

- Tenderness (Algometry) over the initial 72 hours (Algometry AUC₀₋₇₂).

For the comparison of the test gel vs. placebo, the primary efficacy hypothesis to be tested is the equality of Algometry AUC₀₋₇₂, i. e.

$$H_0: \mu_T = \mu_P \text{ vs. } H_1: \mu_T \neq \mu_P.$$

The primary efficacy endpoint will be analyzed using analysis-of-covariance (ANCOVA) with treatment as the factor and baseline tenderness (algometry) as the covariate. Pair-wise comparisons may be made from above model.

The primary analysis population is the Per protocol population (PP).

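### The primary naproxen-versus-placebo test leads with a completers-only Per Protocol set, and neither reading of study completion fits an endpoint that closes at 72 h

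*Protocol*

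**What the plan says.** **Hypothesis.** Protocol 9.1 and SAP 14.4.1 test equality of mean Algometry AUC 0-72 between naproxen gel and placebo. The SAP gives a two-sided alternative.

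**Population.** Protocol 9.3: "The primary efficacy analysis population will be PP population and ITT Population will be secondary". SAP 14.4.1 repeats the choice: "The primary analysis population is the Per protocol population (PP". SAP 14.2, in the same terms as Protocol 9.3, defines the set: "The Per Protocol population will include all subjects in ITT who complete the study and do not have any major protocol violations". The analysis is then repeated on ITT (FAS in the SAP) as a robustness check. PP exclusions are settled before database lock, and deviations are classified at a blinded review (SAP 12).

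**Completion.** The only explicit definition is in Protocol 4.4: "A participant is considered to have completed the study if he/she has completed all phases of the study up to Visit 6". Protocol 6.8, which concerns availability of the study gel, reads "No study intervention will be available after Visit 6 (Day 11"; the schedule contains no such pair of visit and day. Elsewhere the study ends at Visit 11: Protocol 8.1.12 names that visit as end of study, SAP 2 describes participation as running "from randomization (V1) to Final Visit (V11", and SAP 3 gives "and final Visit 11 (120 h after first treatment, Day 6". SAP 14.2 requires completion without defining it. The primary endpoint closes at "Visit 7 (72 h after first treatment, Day 4".

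**Leavers.** Protocol 9.2 allows for 10% drop-out, and Protocol 7.2 expects withdrawal to be uncommon. Under Protocol 7.1, patients who stop the gel stay in the study. SAP 14.8 fills in values after premature termination. SAP 14.10 summarises disposition over all subjects and lists reasons by subject, with no table by arm.

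**The concern.** Randomisation protects a comparison of the patients as randomised. Once the lead analysis keeps only those who stayed, the arms can differ in who is left as well as in treatment. The documents give no reason for leading a comparison against placebo with such a set. Blinded classification prevents analyst-driven exclusions but does nothing about patients who leave because of how they are doing.

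The placebo arm is small: each of its 15 patients is 6.7% of the arm, so two or three leavers are 13% to 20% of it. PP membership decides who enters the primary test, so the unclear completion rule changes the analysed set for anyone who leaves between 60 h and 120 h. Protocol 2.1 says the trial is to guide development of the gel, and the estimate offered for that purpose is the PP one.

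**Working it through.** **1. The plan's own figure.** Protocol 9.2 gives 30:15 patients, 10% drop-out, two-sided 5%, a standardised effect over 1, and power of about 80%. Noncentral t with ncp = d / √(1/n₁ + 1/n₂) and df = n₁ + n₂ − 2, at d = 1:

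- 27:13: ncp = 1/√(0.0370 + 0.0769) = 2.96, df = 38, power 0.823.
- 27:13.5: power 0.833.
- 30:15, nobody lost: power 0.871.

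This is compatible with about 80%. The power statement is not at issue.

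**2. The two completion readings against the endpoint.**

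| Patient | AUC 0-72 data | PP if completion = Visit 6 | PP if completion = Visit 11 |
|---|---|---|---|
| Leaves before Visit 6 (60 h) | incomplete | out | out |
| Attends Visit 6, leaves before Visit 7 (72 h) | 72 h value missing | in, 72 h value imputed | out |
| Attends Visit 7, leaves before Visit 11 (120 h) | fully observed | in | out |

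On the 12-hour trapezoidal grid the 72 h value carries 6/72 = 8.3% of the weight. The Visit 6 reading therefore admits a slightly incomplete endpoint. The Visit 11 reading discards a complete one that needs no imputation.

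**3. An outer bound.** Suppose exactly the worst patients leave, with no baseline adjustment. By simulation, removing the worst 3 of 30 raises an arm's mean by 0.186 SD; removing the worst 1, 2 or 3 of 15 raises it by 0.123, 0.227 or 0.328 SD. With a true effect of 1 SD the PP estimate is 1 + (naproxen shift) − (placebo shift):

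- 3/30 vs 1/15: 1 + 0.186 − 0.123 = 1.06
- 3/30 vs 2/15: 1 + 0.186 − 0.227 = 0.96
- 3/30 vs 3/15: 1 + 0.186 − 0.328 = 0.86

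The more unequal splits 2/30 vs 3/15 and 4/30 vs 0/15 give 0.80 and 1.24.

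**4. Less extreme leaving, ANCOVA with baseline.** Seven-visit trajectories over 0 to 72 h; effect of 1.0 baseline-adjusted SD of the AUC; probability of leaving logistic in the AUC; ranges over several slope, residual, recovery and dependence settings. Every split by arm is an assumption. The nominal null rejection rate is 2.5% per direction.

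| Loss, naproxen vs placebo | PP estimate (SD) | Error rates |
|---|---|---|
| Equal 10% | 0.99–1.01 | power 0.81–0.87; null 2–3% per direction |
| 2/30 vs 3/15 (5/45 = 11.1%) | 0.85–0.97 | power 0.70–0.77, against 0.806 for 28:12 without bias; null 0.5–2.3% for naproxen, 2.9–6.3% for placebo |
| 4/30 vs 0/15 (4/45 = 8.9%) | 1.04–1.16 | null 3–8% for naproxen |
| 6/30 vs 1/15 (7/45 = 15.6%) | 1.04–1.15 | null 3–7% for naproxen |

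Loss at random gave no bias at any split. A second simulation gave about 0.88 SD with power about 0.70 for the second row, and about 1.12 SD with 6% null rejections favouring naproxen for the third.

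**5. What ITT would give (SD).**

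| Loss | SAP 14.8 imputation, all leave by 60 h | SAP 14.8 imputation, leaving spread to 108 h |
|---|---|---|
| Equal 10% | 0.93–0.98 (power 0.65–0.85) | 0.96–0.99 |
| 2/30 vs 3/15 | 0.96–1.14 (null 3–8% for naproxen) | 0.98–1.08 |
| 6/30 vs 1/15 | 0.71–0.93 (power 0.38–0.80) | 0.84–0.97 |

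ITT using leavers' observed visits without single imputation gave 0.96–1.03 SD at every split tested, null rejection of 1.6–2.9% per direction and power of about 0.83–0.89. Those error rates are approximate, because the test used the empirical standard error across simulated trials. With an ordinary ANCOVA on filled-in values, null rejection was 2–4% per direction and power about 0.85–0.89. Power above the no-loss value of 0.871 should not be read as a gain.

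**The case against.** **The harm rests on assumed splits.** True. The documents give one overall rate. Six days of staff-applied treatment, with gel-stoppers kept in the study, point to low loss. Two of the three unequal splits exceed 10%, and the third is extreme. This limits the size of the point. It does not supply a reason for the more selectable set to lead.

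**ITT is repeated and exclusions are fixed blind.** A divergence between PP and ITT would be visible, but the plan makes PP the lead result if they disagree.

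**It is a hypothesis-finding trial.** Protocol 9.4 tests only if deemed necessary, and no decision rule is tied to PP or to p < 0.05. That lowers the stakes. SAP 14.4.1 nevertheless plans the test without that condition, and SAP 14.7 sets the level at 5%.

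**A plain swap to ITT is no clear improvement.** This stands. At equal 10% loss PP does better than ITT with the SAP 14.8 values, and at 2/30 vs 3/15 with early leaving the swap raises false rejections in naproxen's favour. Hence the estimation method must change with the population.

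**Stronger readings that a reader might infer, and that the documents do not support:**

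- *PP flatters naproxen.* The direction depends on which arm loses more; if placebo does, PP understates naproxen.
- *PP removes rescue users and patients who stop the gel.* The completion rule does neither.
- *There are two formal completion definitions.* There is one, in Protocol 4.4, and it conflicts with the end of study elsewhere. Protocol 6.8 concerns gel availability; its visit and day look transposed, but nothing confirms that.

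**Conclusion.** The point holds and should be fixed, with a size that depends on conduct. The primary test against placebo is conditioned on staying in the study, and the completion rule behind it is inconsistent and matched to the endpoint on neither reading. With low, random or near-equal loss nothing material changes. With outcome-related and unequal loss, the PP estimate moves by roughly 0.1 to 0.15 SD either way on a true effect of 1 SD. Exact removal of the worst patients, unadjusted for baseline, is an outer bound at about 0.2 SD or slightly more (0.80 and 1.24).

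This rests on the assumed splits, a true effect of 1.0 SD (the documents say only over 1) and the simulated trajectories. The preference for an observed-visits analysis is firm on bias within those settings; its size and power are approximate.

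**What to change.** 1. **Protocol 9.3, SAP 14.2 and 14.4.1.** Make ITT/FAS primary and PP supportive. Take the primary estimate of AUC 0-72 from all observed visits, for example a repeated-measures mixed model with the AUC as a weighted sum of visit means. With baseline adjusted for, the treatment difference is 12 h × (sum of the differences at 12, 24, 36, 48 and 60 h) + 6 h × (difference at 72 h). Specify the covariance structure, a fallback and a small-sample degrees-of-freedom method in advance, given 15 placebo patients. Keep the SAP 14.8 single-imputation ANCOVA as a sensitivity analysis.
2. **Completion.** Reconcile Protocol 4.4 and 6.8 with Protocol 8.1.12 and SAP 2 and 3, and state one definition in SAP 14.2. Do not exclude patients observed through Visit 7 from the AUC 0-72 analysis only because they left later. Settling on Visit 11 while PP stays primary would exclude more leavers.
3. **SAP 14.10.** Tabulate disposition, reasons for discontinuation and PP exclusions by arm. This is a reporting refinement.

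**Cost.** One extra model and no new data; both populations are already planned, and SAP 1 leaves the SAP open until after the blind review. A protocol amendment may be needed, since Protocol 9.3 was last changed in a substantial amendment and Protocol 10.1.1 sends substantial modifications to the authorities. The ITT set still requires one efficacy measure after the first application, so it is not every randomised patient.

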9.4 Statistical Analyses - Amended

The statistical analysis plan (SAP) will be finalized prior to database lock and it will include a more technical and detailed description of the statistical analyses described in this section. This section is a summary of the planned statistical analyses of the most important endpoints including primary, secondary, and other key endpoints.

9.4.1 General Considerations

Statistical analysis will be performed using statistical analysis system and the version used will be specified in the Statistical Analysis Plan (SAP) and placed on file. The SAP will contain a more comprehensive explanation than described below of the methodology used in the statistical analyses. The SAP will also contain the rules and data handling conventions used to perform the analyses, and the procedure used for accounting for missing data.

All endpoints will be summarized descriptively by treatment. Statistical testings may be conducted at significance level of 0.05 if deemed necessary and no multiplicity adjustment will be made.

9.4.2 Primary Endpoint

The primary efficacy variable is:

- Tenderness (Algometry) over the initial 72 hours (Algometry AUC 0-72).

The primary efficacy endpoint will be analyzed if deemed necessary using analysis of covariance (ANCOVA) with treatment as the factor and baseline tenderness (algometry) as the covariance. Pair-wise comparisons may be made from above model.

9.4.3 Secondary Endpoint

- Safety (percentage of subjects with at least one TEAE).
- The secondary endpoint will be summarized descriptively by body system and preferred term.

9.4.4 Other Endpoints

- VAS POM over the initial 12-hours (VAS AUC 0-12), 24-hours (VAS AUC 0-24), 36-hours (VAS AUC 0-36), 48-hours (VAS AUC 0-48), 60-hours (VAS AUC 0-60), 72-hours (VAS AUC 0-72), and 120 hours (VAS AUC 0-120);
- Change of VAS POM at hours 12, 24, 36, 48, 60, 72 and 120 from baseline;
- Change of Algometric Tenderness (N/cm^2) at hours 12, 24, 36, 48, 60, 72 and 120 from baseline;
- Algometric Tenderness (N/cm^2) over the initial 12-hours (N/cm^2 AUC 0-12), 24-hours (N/cm^2 AUC 0-24), 36-hours (N/cm^2 AUC 0-36), 48-hours (N/cm^2 AUC 0-48) 60-hours (N/cm^2 AUC 0-60) and 120 hours (N/cm^2 AUC 0-120);
- Ratio of algometry injured/contralateral sites over 72 hours and 120 hours (N/cm^2 Ratio AUC 0-72 and N/cm^2 Ratio AUC 0-120);
- Percent of subjects with no (zero) VAS POM at 120 hours;
- Global assessment of treatment efficacy at 24 hours, 48 hours, 72 hours and 120 hours by patients using a 5-point scale (0=none, 1=poor, 2=fair, 3=good, 4=excellent);

- Global assessment of treatment efficacy at 24 hours, 48 hours, 72 hours and 120 hours by investigators using a 5-point scale (0=none, 1=poor, 2=fair, 3=good, 4=excellent).

9.4.5 Safety Analysis

Safety will be measured by adverse events (AEs) and vital signs. Only descriptive analyses will be conducted on the Safety Population. No imputation will be made for missing safety data. Quantitative data for safety variables will be described by summary statistics for the original data as well as for the differences to baseline when it is appropriate. Frequency tables will be provided for qualitative data. No statistical test will be planned regarding the safety analyses.

Only treatment-emergent AEs will be included in the summary analysis, i.e., AEs that begin or worsen after the first application of Investigational Medicinal Product (IMP). The number and percent of subjects who experience any event and the number of events overall, by System Organ Class, and by Preferred Term will be displayed by treatment group. Tables will also be produced by severity and relationship to IMP. Seriousness, severity, relationship to IMP duration, and outcome will also be listed.

Listings of individual data will be presented.

9.5 Interim Analysis

No interim analysis is planned for this study.

10. Supporting Documentation and Operational Considerations

10.1.1 Regulatory and Ethical Considerations

- This study will be conducted in accordance with the protocol and with the following:
 - Consensus ethical principles derived from international guidelines including the Declaration of Helsinki and Council for International Organizations of Medical Sciences (CIOMS) International Ethical Guidelines
 - Applicable ICH Good Clinical Practice (GCP) Guidelines
 - Applicable laws and regulations
- The protocol, protocol amendments, ICF, Investigator Brochure and other relevant documents (e.g., advertisements) must be submitted to an IRB/IEC by the investigator and reviewed and approved by the IRB/IEC before the study is initiated.
- Any amendments to the protocol will require IRB/IEC approval before implementation of changes made to the study design, except for changes necessary to eliminate an immediate hazard to study participants. Any substantial modification of the protocol will be submitted to the competent authorities as substantial amendments for approval, in accordance with ICH Good Clinical Practice and national and international regulations.
- Protocols and any substantial amendments to the protocol will require health authority approval prior to initiation except for changes necessary to eliminate an immediate hazard to study participants.
- The investigator will be responsible for the following:
 - Providing written summaries of the status of the study to the IRB/IEC annually or more frequently in accordance with the requirements, policies, and procedures established by the IRB/IEC
 - Notifying the IRB/IEC of SAEs or other significant safety findings as required by IRB/IEC procedures
 - Providing oversight of the conduct of the study at the site and adherence to requirements of ICH guidelines, the IRB/IEC, and all other applicable local regulations

